1.5 Study Rationale

ONC201 is a small molecule which selectively targets the G protein-coupled receptor DRD2. Downstream of target engagement, ONC201 activates the integrated stress response (ISR) in tumor cell leading to inactivation of Akt and ERK signaling as well as

induction of the TRAIL pathway [24]. These pathways are highly deregulated in a majority of Type II EC patients. ONC201 also inhibits dopamine receptor 2 (DRD2), resulting in anti-tumor responses in preclinical models [24]. Furthermore, DRD2 expression was several fold higher in endometrial adenocarcinoma when compared to normal endometrium.

Single agent ONC201 has been examined in open-label Phase I studies in patients with advanced, treatment refractory solid malignancies [24, 25]. Due to its differential antiproliferative and pro-apoptotic response in tumor cells, treatment was overall well tolerated, and the recommended phase II dose of ONC201 was set at 625mg every three weeks. An additional dose-escalation phase I study (NCT02609230) is further evaluating weekly versus three-week dosing in patients with advanced solid tumors and multiple myeloma. Preliminary data from these phase I studies suggests a possible clinical benefit in patients with advanced, chemo-refractory endometrial cancers, with at least one mixed response noted in a patient with clear cell histology [17].

We hypothesize that single agent ONC201 will demonstrate clinical benefit in women with recurrent or metastatic type II endometrial cancers.

Systemic exposure with once per week dosing in patients results in concentrations that exceed the 1,000ng/mL threshold for ~24 hours. In vitro studies indicate that maximum antiproliferative and pro-apoptotic effects of ONC201 can require continuous incubation for at least 48 hours in some cancer cell lines. This generated the hypothesis that

consecutive day dosing could maintain therapeutic concentrations for >48 hours. As summarized in Section 1.4.3, PK results from a Phase I/II indicate that twice per administration of ONC201 on two consecutive days maintains >1,000ng/mL systemic concentrations for >72 hours in patients who received 375mg or 625mg. Given the safety profile of ONC201 and these findings, the safety of twice per week dosing on two consecutive days will be evaluated in this clinical trial in addition to weekly dosing.

1.6 **Correlative Testing**

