2.4 Secondary Endpoints

- Safety profile of ONC201 will be determined by type, frequency, severity and timing and relationship of Adverse Events and lab abnormalities to ONC201.
- Duration of response and duration of stable disease will be determined by the time-period when a response is first seen or stable disease until disease progression.
- Overall response rate will be determined by RECIST version 1.1. Median PFS will be calculated as the period between the start of the treatment until disease progression.
- Study drug concentration in tumor tissues from patients taking once per week or twice per week on two consecutive days, about 24 hours after the single dose or second dose respectively.

3 Study Plan

We propose a Simon two-stage, non-randomized, open label, Phase II trial of ONC201 in women with metastatic or recurrent Type II endometrial cancer who failed at least 1 prior chemotherapy regimen. Patients with histologically confirmed Type II endometrial cancer,

including but not limited to serous, clear cell, carcinosarcoma, adenosquamous, and mixed histologies, will be eligible.

Arm A and C will enroll 6 evaluable patients each. All subjects in Arm A will have a biopsy of their tumor one day after the second dose of ONC201 on Cycle 1 Day 9. All subjects in Arm C will have a biopsy of their tumor one day after the 4th dose of ONC201 on Cycle 1 Day 10.

Arm B will enroll 10-24 evaluable patients.

ONC201 will be administered at a dose of 625 mg by mouth, once or twice each week until disease progression, unacceptable toxicity, or if the patient discontinues for any other reason.

It is anticipated that enrollment into this study will complete in 24 months.

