4.6 Subject Registration

In order to begin the patient registration process, the site must obtain a slot for the candidate patient from Oncoceutics. At the time of receipt of the signed consent form, Oncoceutics medical monitor must be notified via email to initiate eligibility review. The study staff must include de-identified patient source documentation, the completed New Patient Registration Form (provided by Oncoceutics) and a tentative therapy start date. Correspondence from the Sponsor for patient registration approval will be granted within 48 hours of receipt of adequate documentation.

Registration approval will be valid for 7-business days from receipt of approval. If the potential patient is not treated within those 7 business days, a new registration form must be submitted to determine eligibility.

A patient identifier will be assigned at the time of approval. Screening and eligibility MUST be entered into Redcap EDC within 7-business days of screening visit.

5 Treatment Plan

Treatment will be administered on an outpatient basis. Treatment will be administered as described below. Dose delays and modifications should only be done following protocol guidelines described in section 6.0. If treatment delays are more than 14 days due to toxicity study therapy will be discontinued.

Regimen description					
Arm	Agent	Dose	Route	Schedule	Cycle Length
A & B	ONC201	625mg	Oral	Once per week	3 weeks
С	ONC201	625mg	Oral	Twice per week on two	3 weeks
				consecutive days	

5.1 **Treatment Administration**

One treatment cycle will be defined as 21 days, corresponding to 3 doses of ONC201 (i.e., one cycle is 3 weeks) for Arm A and B or 6 doses in Arm C. Beyond cycle 1 week 1 dose(s), ONC201 capsules will be dispensed on day 1 of every cycle thereafter to be taken at home. Patients must complete study drug diary to keep a log of the drug intake. Any unused drug should be returned to the site. Any missed doses should be recorded. At home patients must take the drug as indicated, however if the drug is missed for reasons not related to adverse events +/- 2 days are allowed. The capsules should be swallowed as whole and should not be chewed or broken.

Patients should take designated capsules of ONC201 at approximately the same time on each drug administration. Patients will be instructed to not eat for 2 hours pre and 2 hours post dosing. If the patient vomits after taking ONC201, they should not retake the dose.

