12.2 Analysis of Secondary/Exploratory Endpoints

All patients enrolled in the study who received at least 1 dose of ONC201 will be evaluated in the safety analysis using descriptive statistics including pre-treatment characteristics and concomitant treatment.

Adverse events and clinical labs will be graded according to NCI CTCAE Version 4.03. For labs without CTC grade definitions, results will be summarized as normal, abnormal or not done. Summary tables will present frequencies of patients experiencing at least one AE categorized by System Organ Class and Preferred Term according to MedDRA terminology. Listings will be prepared for each laboratory measure, and will be structured to permit review of the data by patient as they progress on treatment. Graphic displays and shift tables may be provided, as appropriate, to illustrate the results over time on study. ONC201 dose delays, dose modifications, drug exposure and duration of treatment will be also summarized.

Duration of response and duration of stable disease will be characterized using Kaplan-Meir estimates in the relevant subgroups.

Progression Free Survival (PFS) will be characterized using Kaplan-Meier curves. Median PFS will be calculated along with 95% confidence intervals. Patients who are lost to follow-up (who withdraw from the study prior to evidence of progression or death) will be censored.

12.3 **Reporting and Exclusions**

12.3.1 Evaluation of toxicity:

All patients will be evaluable for toxicity from the time of their first treatment with ONC201. Safety will be assessed by quantifying the toxicities and grades experienced by subjects who have received ONC201, including serious adverse events (SAEs). Other safety endpoints include laboratory safety assessments, vital signs and physical examinations.

A Bayesian method [27] will be used for toxicity monitoring based on the dose-limiting toxicity (DLT) rate. Patients in Arm A and Arm B will be monitored jointly for toxicity. Toxicities will be defined according to the Common Terminology Criteria for Adverse Events (CTCAE) version 4.03. DLT is defined as a clinically significant adverse event or abnormal laboratory value assessed as unrelated to disease progression, intercurrent illness, or concomitant medications and occurring during the first cycle on study that meets any of the following criteria:

- CTCAE grade 3 AST (SGOT) or ALT (SGPT) for > 7 days
- CTCAE grade 4 AST (SGOT) or ALT (SGPT) of any duration

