- All other clinically significant NCI common terminology criteria that are CTCAE grade \geq 3 (except for electrolyte disturbances responsive to correction within 24 h, diarrhea, nausea and vomiting that responds to standard medical care)

An AE must be clinically significant to define DLT e.g. nausea and vomiting < grade 3, alopecia, study drug-related fever, electrolyte abnormalities (including K, Na, Cl, HCO3, Mg, Ca, bilirubin) that are grade <3 will not define the DLT.

Monitoring for toxicity will follow a Bayesian-based rule for the probability that the rate of DLT exceeds a maximal tolerated level of 33%. We will assume a Beta (1,2) prior,

which is prior information equivalent to one DLT observed in three treated patients. This minimally informative prior is justified as there is some clinical experience with the investigational therapy. Early termination for toxicity will be considered based on a posterior probability above 75% that the toxicity rate exceeds 33%. Stopping boundaries for toxicity monitoring are provided in the table below.

# Patients (inclusive)	Stop the trial if there are at least this many DLTs total:
1 to 2	Never stop with this many patients
3	2
4 to 6	3
7 to 9	4
10 to 12	5
13 to 15	6
16 to 18	7
19 to 21	8
22 to 24	9
25 to 27	10
28 to 29	11
30	Always stop with this many patient

12.3.2 Evaluation of response:

Only those patients who have measurable disease present at baseline, have received at least two cycles of therapy, and have had their disease re-evaluated will be considered evaluable for response. Each patient will be assigned one of the following categories: 1) complete response, 2) partial response, 3) stable disease, 4) progressive disease, 5) early death from malignant disease, 6) early death from toxicity, 7) early death because of other cause, or 9) unknown (not assessable, insufficient data). [Note: By arbitrary convention, category 9 usually designates the "unknown" status of any type of data in a clinical database.]

Patients in response categories 4-9 should be considered to have a treatment failure (disease progression). An incorrect treatment schedule or drug administration does not result in exclusion from the analysis of the response rate.

13 Data Reporting / Regulatory Requirements

Adverse event lists, guidelines, and instructions for reporting adverse events can be found in Section 10.

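### Section 12.3.1 states the DLT stopping rule for Arms A and B only and gives no arm-level boundary for Arm C, which takes twice the weekly dose

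*Combined protocol and SAP*

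**What the plan says.** Section 12.3.1 first makes every treated patient evaluable for toxicity. It then introduces a Bayesian rule on the cycle 1 DLT rate and adds: "Patients in Arm A and Arm B will be monitored jointly for toxicity". The prior is Beta(1,2) and the tolerated DLT rate is 33%. The action rule reads "Early termination for toxicity will be considered based on a posterior probability above 75% that the toxicity rate exceeds 33" percent. The table column is headed "Stop the trial if there are at least this many DLTs total" and its rows run from 1 to 30 patients.

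The Study Summary plans 6, 24 and 6 patients in Arms A, B and C. Section 5.1 defines a 21-day cycle as "corresponding to 3 doses of ONC201 (i.e., one cycle is 3 weeks) for Arm A and B or 6 doses in Arm C", each dose being 625 mg. Section 1.5 says that "the safety of twice per week dosing on two consecutive days will be evaluated in this clinical trial in addition to weekly dosing".

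For Arm C the plan otherwise provides the holds and reductions of Table 6.1, SAE reporting within 24 hours (section 10.2), descriptive safety summaries (section 12.2) and sponsor control of entry, since "the site must obtain a slot for the candidate patient" (section 4.6).

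**The concern.** The arm with the greater exposure is the one for which no DLT boundary is stated. Section 1.4.3 reports that consecutive-day dosing at 375 mg or 625 mg kept plasma levels above 1,000 ng/mL for more than 72 hours, against generally less than 24 hours with weekly dosing. That section covers leukemia and myelodysplastic syndrome patients and gives pharmacokinetics only, so it does not settle tolerability in this population.

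Without a boundary, nothing in the plan adds up DLTs across Arm C and says when to pause. At stake is how many of the last Arm C patients would be dosed after the earlier ones had already shown an unacceptable rate.

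**Working it through.** **Inputs.** Section 12.3.1: prior Beta(1,2), threshold 0.33, cutoff 0.75, printed table. Study Summary: 6, 24 and 6 patients. Section 5.1: 3 or 6 doses of 625 mg per 21 days.

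**Scope and dose.** 6 + 24 = 30, the last table row; all three arms would be 36. Per week: 625 mg against 2 × 625 = 1250 mg. Per cycle: 3 × 625 = 1875 mg against 6 × 625 = 3750 mg.

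**Posterior.** With x DLTs in n patients the DLT rate follows Beta(1+x, 2+n−x). For 6 of 6 this is Beta(7,2), and P(rate > 0.33) = 1 − (8 × 0.33^7 − 7 × 0.33^8) = 1 − (0.00341 − 0.00098) = 0.998. Similarly:

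| DLTs / patients | P(rate > 0.33) | Worded rule | Printed table |
|---|---|---|---|
| 2 / 2 | 0.892 | crosses | never stops |
| 2 / 3 | 0.795 | crosses | stops |
| 2 / 4 | 0.687 | no | no |
| 3 / 4 | 0.903 | crosses | stops |
| 2 / 5 | 0.578 | no | no |
| 3 / 5 | 0.832 | crosses | stops |
| 3 / 6 | 0.748 | no | stops |
| 4 / 6 | 0.915 | crosses | stops |

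At Arm C's sizes, rule and table agree for n = 3 to 5 and differ at n = 2 and n = 6. Over n = 3 to 29, the worded 33% and 75% fail to reproduce 16 of the 27 printed boundaries. A 30% threshold with the 75% cutoff reproduces all 27.

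**Chance that Arm C crosses, with boundaries 2 of 3 and 3 of 4 to 5.** At true DLT rate p:
- First crossing at n = 3: 3p²(1−p) + p³.
- At n = 4: zero, because 3 of 4 requires at least 2 of the first 3.
- At n = 5: 3p(1−p)² × p².
- Extra with the printed n = 6 row (3 DLTs): 7p³(1−p)³. With the worded n = 6 boundary (4 DLTs): zero.

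**Patients spared.** At most 3 × P(cross at 3) + 1 × P(cross at 5). This assumes that the next patient always waits for the previous cycle 1 result and that a crossing does end enrolment.

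| True rate | Cross at 3 | Cross at 5 | Total | Total with printed n = 6 row | Spared, at most |
|---|---|---|---|---|---|
| 10% | 0.028 | 0.002 | 0.030 | 0.036 | 0.09 |
| 20% | 0.104 | 0.015 | 0.119 | 0.148 | 0.33 |
| 33% | 0.255 | 0.048 | 0.303 | 0.379 | 0.81 |
| 50% | 0.500 | 0.094 | 0.594 | 0.703 | 1.59 |
| 60% | 0.648 | 0.104 | 0.752 | 0.848 | 2.05 |
| 70% | 0.784 | 0.093 | 0.877 | 0.941 | 2.44 |

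If all six patients start within 21 days, none is spared.

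**Does the A+B rule protect Arm C indirectly?** Because the table says to stop the trial, a crossing in A+B could end Arm C as well. Running the printed table over n = 3 to 29, the chance of crossing is 0.009, 0.040 and 0.212 at true A+B rates of 5%, 10% and 20%. As written, those crossings depend on weekly-dosing DLTs, so they say little about toxicity specific to the two-day schedule.

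**The case against.** The text is silent on Arm C; it does not expressly exclude it. The Study Summary describes Bayesian DLT monitoring without limiting it to any arm, and the sentence on joint monitoring could mean only that the two arms on the same schedule are pooled, with Arm C run separately on the same table. That reading is possible, but nothing states it, and a table ending at 30 fits A+B. What stands is that the accurate wording is that no boundary is stated for Arm C.

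A reader might also infer that Arm C has no safety oversight, or that the two-day schedule is known to be toxic. The documents support neither. Table 6.1, 24-hour SAE reporting and slot approval apply to Arm C, and section 1.5 cites the drug's safety profile in support of the schedule. No text available for review suggests a high DLT rate there, although the Investigator's Brochure and the part of section 1.4 between 1.4.1 and 1.4.3 were not available.

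It is also fair to say that the gain is small at plausible rates, that a crossing leads only to termination being considered, and that enrolment holds are not required for Arms A and B. All of this stands, and it limits the weight of the point. It does not supply the missing boundary.

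**Conclusion.** The gap is real. Followed as written, no number of DLTs in Arm C reaches a stated boundary, although evaluating that schedule's safety is a declared purpose. It should be closed because closing it is cheap. Section 12.1 restricts the primary endpoint to Arm B, so a reader who inferred that the efficacy conclusion is compromised would be going beyond the documents.

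The benefit depends on the unknown Arm C DLT rate: a fraction of a patient at rates up to the tolerated 33%, and 1.6 to 2.4 of 6 patients at 50% to 70%. Those figures are upper limits that assume staggered dosing and a stop at crossing, and the higher rates are illustrations without support in the document.

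**What to change.** In section 12.3.1, state that:
- Arm C is monitored as a separate stream under the same DLT definition, prior and cutoff, with termination of Arm C considered at 2 DLTs in 3 patients or 3 DLTs in 4 to 5;
- at n = 2 and n = 6, either the worded rule or the printed table applies, naming which (the table fits a 30% threshold, so settle whether 30% or 33% is meant);
- a crossing in A+B does or does not stop Arm C, and a crossing in Arm C does or does not stop A+B.

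The cost is a few sentences and two boundary rows. AE grade, timing and attribution are already collected, so the only new work is applying the DLT definition to Arm C's cycle 1 events. Needless reviews would occur in about 3%, 12% and 30% of cases at true rates of 10%, 20% and 33%, or 4%, 15% and 38% with the printed n = 6 row.

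Optionally, hold patients 4 and 6 until the cycle 1 windows of patients 3 and 5 have closed. That means at most two waits of up to 21 days. It is best applied by withholding the slot, because "Registration approval will be valid for 7-business days from receipt of approval" and an approved patient who waits longer needs a new form. Without such holds the saving shrinks, to nothing if all six start within 21 days.

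### The printed DLT stopping boundaries do not follow from the stated Bayesian rule: they are one DLT too low at 16 of 27 sample sizes

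*Combined protocol and SAP*

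**What the plan says.** Section 12.3.1 (Evaluation of toxicity) fixes every element of the monitoring rule.

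- Population: "Patients in Arm A and Arm B will be monitored jointly for toxicity". With 6 patients in Arm A and 24 in Arm B, that is 30 patients.
- Prior: "We will assume a Beta (1,2) prior", described as "which is prior information equivalent to one DLT observed in three treated patients".
- Limit: the rule concerns the probability that "the rate of DLT exceeds a maximal tolerated level of 33"%.
- Cut-off: "Early termination for toxicity will be considered based on a posterior probability above 75% that the toxicity rate exceeds 33"%.

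The section then presents a table as the boundaries for this monitoring. Its column heading is "Stop the trial if there are at least this many DLTs total", and its patient ranges are marked as inclusive. The boundaries are 2 (n = 3), 3 (4–6), 4 (7–9), 5 (10–12), 6 (13–15), 7 (16–18), 8 (19–21), 9 (22–24), 10 (25–27) and 11 (28–29). The row for 1 to 2 patients reads "Never stop with this many patients", and at 30 patients accrual ends. Numeric boundaries therefore cover 27 sample sizes, n = 3 to 29.

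**The concern.** Given a prior, a limit and a cut-off, the boundary at each sample size is fully determined. The printed table steps up by one DLT every three patients, which is slower than a 33% limit with a 75% cut-off should allow as the numbers grow. If the table does not come from the stated rule, the trial has two toxicity-stopping thresholds, and the same data can satisfy one and not the other. The section does not say which prevails. The text speaks of considering termination, while the table column is worded as an instruction to stop.

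**Working it through.** **Inputs**, all from Section 12.3.1: prior Beta(1,2); limit 0.33; stop when the posterior probability exceeds 0.75; printed boundaries for n = 3 to 29.

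**Formula.** After x DLTs in n patients the posterior is Beta(1 + x, 2 + n − x). The rule's boundary is the smallest x with P(rate > 0.33) > 0.75. For whole-number parameters this tail equals a binomial sum: P(rate > 0.33) = P(Bin(n + 2, 0.33) ≤ x).

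**One entry by hand, n = 9.** The table stops at 4 DLTs. The posterior is Beta(5, 7), and P(Bin(11, 0.33) ≤ 4) = 0.0122 + 0.0662 + 0.1630 + 0.2408 + 0.2372 = 0.719 (rounded terms). That is below 0.75. Adding the term for 5 DLTs, 0.1636, gives 0.883. The rule's boundary at n = 9 is therefore 5.

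**All 27 entries.** The table agrees with the rule at 11 sample sizes (n = 3, 4, 5, 7, 8, 10, 11, 13, 16, 19, 22). It differs at these 16:

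| n | Printed | Stated rule | Posterior at printed boundary |
|---|---|---|---|
| 6 | 3 | 4 | 0.748 |
| 9 | 4 | 5 | 0.719 |
| 12 | 5 | 6 | 0.699 |
| 14 | 6 | 7 | 0.747 |
| 15 | 6 | 7 | 0.685 |
| 17 | 7 | 8 | 0.731 |
| 18 | 7 | 8 | 0.673 |
| 20 | 8 | 9 | 0.719 |
| 21 | 8 | 9 | 0.664 |
| 23 | 9 | 10 | 0.708 |
| 24 | 9 | 10 | 0.657 |
| 25 | 10 | 11 | 0.746 |
| 26 | 10 | 11 | 0.699 |
| 27 | 10 | 11 | 0.650 |
| 28 | 11 | 12 | 0.737 |
| 29 | 11 | 12 | 0.692 |

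**Attempts to rescue the table.**

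- Rounding the posterior to two decimals and accepting 0.75 removes n = 6, 14 and 25; 13 mismatches remain.
- Reading 33% as 1/3 adds n = 22, giving 17 mismatches.
- Keeping the 33% limit and changing the cut-off anywhere from 50% to 95% never reproduces the table. The best case, a cut-off of about 65%, still fails at n = 4 and 7.
- Changing the limit as well does reproduce all 27 rows, but not uniquely: 28% with 82%, 29% with 80%, 30% with 75% and 31% with 73% all fit. The table is thus a coherent output of some other rule, and its origin cannot be established from the documents.

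**The first row.** At 2 DLTs in 2 patients the posterior is P(Bin(4, 0.33) ≤ 2) = 0.892, so the stated rule is met where the table rules out stopping. The text gives no minimum number of patients. This is separate from the 16.

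**Effect on the chance of stopping.** Exact recursion on the DLT count, a look after each patient from n = 3, accrual to n = 29:

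| True DLT rate | Table | Stated rule |
|---|---|---|
| 5% | 0.9% | 0.8% |
| 10% | 4.0% | 3.3% |
| 15% | 10% | 8% |
| 20% | 21% | 16% |
| 25% | 36% | 28% |
| 30% | 54% | 44% |
| 33% | 65% | 54% |

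The 2-in-2 conflict does not alter these totals, because 2 DLTs also stop at n = 3.

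**The case against.** The arithmetic is not in dispute; the weight to give it is.

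- **Direction and size.** From n = 3 every discrepancy stops earlier, by one DLT. Following the table exposes no one to more toxicity than the stated rule would. At true rates of 5% and 10% the two versions differ by less than one percentage point. The large gaps arise near the level the protocol itself calls maximal tolerated, and the documents give no expected DLT rate. All of this stands, and it limits the harm.
- **Accrual may end early.** Arm B stops after 10 evaluable patients if fewer than 5 are progression-free at 2 months, with a stated probability of 63.3% under the null hypothesis. With 6 patients in Arm A, joint accrual would then end near 16, ignoring replacements and enrolment during the interim. Only 5 of the 14 boundaries for n = 3 to 16 differ, two of them near-ties. To n = 16 the chance of stopping is 19.5% v 15.6% at a true rate of 20%, and 46% v 39% at 30%. This is a fair qualification: the figures to n = 29 assume full accrual. The gap shrinks but does not close.
- **The look schedule.** A boundary for every n most naturally means a look after each patient, as assumed above. No schedule is written. If looks came only every 3 patients, which is an assumption, the gap would be wider: 21% v 13% at 20% and 54% v 37% at 30%.
- **The table is explicit, so staff have something to apply.** That is true, and the first row may simply be an intended minimum of 3 patients. But the text states a different criterion for the same decision, and nothing gives the table precedence.

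**Conclusion.** The concern holds. The printed boundaries are not those of the stated rule: 16 of 27 are one DLT too low, and at least 13 of these cannot be put down to rounding. With 4 DLTs in 9 patients, 5 in 12 or 10 in 27, the table says stop while the written criterion is not met.

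The practical cost is a higher chance of halting Arms A and B when the stated criterion is not satisfied. It is about 5 percentage points at a true DLT rate of 20% and 10 to 11 points at 30% to 33%, given looks after each patient and accrual to 29. It is smaller if Arm B ends at stage 1 and negligible at low DLT rates. The count of mismatches needs no such assumptions; it follows from the prior, limit and cut-off in Section 12.3.1.

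The Simon boundaries and the sample size are untouched. Even so, a trial-stopping threshold cannot stand in two versions, so this must be corrected.

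**What to change.** Reconcile the text and the table in Section 12.3.1. The sponsor should state which is intended and then make the prior, limit, cut-off and printed boundaries agree. This review takes no view on which version is right.

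While the section is open, three secondary points would remove the remaining ambiguity:

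- state in the text the minimum number of patients before monitoring applies, and when the looks occur;
- say whether crossing a boundary stops the trial or prompts a decision;
- report the stopping probabilities of the retained rule over a range of true DLT rates, including low ones.

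The cost is one corrected table or a few words, plus a short table of stopping probabilities. No patients or procedures are added.

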11.1 Response Evaluation Criteria in Solid Tumors (RECIST)

The Response Evaluation Criteria in Solid Tumors (RECIST v 1.1) criteria will be used for objective tumor response assessment. Response assessment would be performed at C3D1, C5D1 and at the end of every 3 cycles beyond cycle 5. All patients, including those removed from the study due to unacceptable toxicity, would undergo radiologic tumor assessment at the time of discontinuation (End of treatment). Patients who show disease progression at the first instance could continue to receive the treatment for up to 2 more cycles if the increase in tumor burden is up to 30%. Patients who continue treatment beyond

progression would undergo another confirmatory scan at the end of 2 more cycles, and if the progression is confirmed, they will be come off the study.

11.2 **Definitions**

Evaluable for adverse events. All patients will be evaluable for adverse events from the time of their first treatment with ONC201.

Evaluable for progression-free survival. All Arm B patients who have received at one dose of ONC201 will be considered evaluable for progress-free survival as the primary endpoint.

Evaluable for objective response. Only those patients who have measurable disease present at baseline, have received at least one cycle of therapy, and have had their disease reevaluated will be considered evaluable for response. These patients will have their response classified according to the definitions stated below. (Note: Patients who exhibit objective disease progression prior to the end of cycle 1 will also be considered evaluable.)

Evaluable Non-Target Disease Response. Patients who have lesions present at baseline that are evaluable but do not meet the definitions of measurable disease, have received at least one cycle of therapy, and have had their disease re-evaluated will be considered evaluable for non-target disease. The response assessment is based on the presence, absence, or unequivocal progression of the lesions.

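### Sections 11.2 and 12.3.2 define the response-evaluable set differently, and no text says which patients form the ORR denominator

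*Combined protocol and SAP*

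**What the plan says.** The protocol (the combined protocol and SAP) lists ORR by RECIST 1.1 as a secondary endpoint in Section 2.4, without a denominator. Section 12.2 covers safety, duration of response, duration of stable disease and PFS, but gives no ORR analysis.

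Two places define who is evaluable for response. Both are worded as exclusive, and both require measurable disease at baseline.

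- Section 11.2: patients must "have received at least one cycle of therapy, and have had their disease reevaluated will be considered evaluable for response". A note adds: "Patients who exhibit objective disease progression prior to the end of cycle 1 will also be considered evaluable".
- Section 12.3.2: patients must "have received at least two cycles of therapy, and have had their disease re-evaluated will be considered evaluable for response". It has no exception for early progression.

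Section 12.3.2 goes on to assign every patient a response category. Categories 5 to 7 are early deaths and category 9 is unknown or not assessable (no category 8 is listed). It then states: "Patients in response categories 4-9 should be considered to have a treatment failure (disease progression". Its closing sentence reads: "An incorrect treatment schedule or drug administration does not result in exclusion from the analysis of the response rate".

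On timing, Section 11.1 says: "Response assessment would be performed at C3D1, C5D1 and at the end of every 3 cycles beyond cycle 5". It also says that all patients, including those removed for toxicity, "would undergo radiologic tumor assessment at the time of discontinuation (End of treatment".

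**The concern.** Two analysts following different sections could report different response rates from the same data, and each could cite the protocol. The patients on whom the rules disagree are not a random subset. They are those who progressed, stopped or died early, so the choice of rule moves the rate in a predictable direction. The study is open label and Section 13.2.1 gives the sponsor all the statistical analysis, so a denominator left open can be settled after the results are known. The stake is the credibility of the reported ORR. No formal decision depends on it.

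**Working it through.** The plan states no ORR target, sample size or power, so there is no figure to reproduce. The check compares the rules and then illustrates the size.

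**Step 1. Who is in each set**

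| Patient | Section 11.2 | Section 12.3.2 filter | Section 12.3.2 category |
|---|---|---|---|
| Two or more cycles, re-evaluated | in | in | by result |
| At least one but fewer than two cycles, re-evaluated | in | out | by result |
| Objective progression before the end of cycle 1, then stops | in | out | 4, failure |
| Dies or leaves before completing two cycles, never re-evaluated | out | out | 5-7 or 9, failure |

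The 12.3.2 set lies inside the 11.2 set. Rows 2 and 3 separate the two definitions. Row 4 separates both of them from a denominator of all patients.

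**Step 2. Direction**

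A cycle is 21 days, so the first scheduled response scan, C3D1, falls on day 2 × 21 + 1 = 43. A patient who leaves before completing two cycles could show a response only on an unscheduled or end-of-treatment scan. Almost all such patients will therefore be non-responders. Dropping k non-responders from N patients with x responders gives

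ORR = x / (N − k), that is, x/N multiplied by N / (N − k) ≥ 1.

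The rate could fall only if a dropped patient had responded.

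**Step 3. Size**

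The documents do not give k or x. Assume N = 24 treated (the Arm B target) and x = 3. Intervals are exact (Clopper-Pearson) 95%.

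| k | ORR | 95% CI | Multiplier |
|---|---|---|---|
| 0 | 3/24 = 12.5% | 2.7-32.4 | 1.00 |
| 2 | 3/22 = 13.6% | 2.9-34.9 | 24/22 = 1.09 |
| 4 | 3/20 = 15.0% | 3.2-37.9 | 24/20 = 1.20 |

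One dataset can produce all three rows. Suppose one patient dies before any re-evaluation, one withdraws without a scan, and two stop in cycle 2 with an end-of-treatment scan showing progression. All treated gives 3/24. Section 11.2 drops the first two and gives 3/22. Section 12.3.2 drops all four and gives 3/20.

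**Step 4. Sensitivity of the example**

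- Sections 3 and 11.1 let some patients continue after a first progression. If one of the two cycle-2 patients completes two cycles that way, Section 12.3.2 gives 3/21 = 14.3% (3.0-36.3).
- Section 3 accepts a scan already made within 30 days of the end of treatment. If neither cycle-2 patient has a new scan, neither has been re-evaluated. Section 11.2 then also gives 3/20, and both definitions depart from all treated by the same amount.
- If the 36 planned patients (6 + 24 + 6) were pooled, k = 4 would give a multiplier of 36/32 = 1.125.

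**The case against.** Four points on the other side deserve weight.

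First, a reader might infer that Section 12.3.2 contradicts itself, because its filter excludes patients whom its categories count as failures. The text does not prove that. If the category sentence covers all patients and evaluable is a subset, the two statements can stand together. A death after two cycles and a scan would also pass the filter, since early death is undefined. What remains is an ambiguity: on either reading, the section does not say which group is the denominator. The closing sentence leans towards inclusion, but it concerns incorrect schedule or administration, not early death or missing scans.

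Second, a reader might infer that the sets split even for patients scanned on schedule, because a 7-day imaging window around C3D1 allows a scan on day 36. The documents do not support this. Neither definition requires the scan to follow the last required cycle. The last cycle-2 dose in Arms A and B is itself due on day 21 + 15 = 36, and the protocol does not say whether receiving two cycles means doses or elapsed days.

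Third, the gap between the two written definitions is small: 1.4 percentage points in the example (13.6% against 15.0%). The wider span of 12.5% to 15.0% brings in the all-treated denominator, which is neither evaluability rule. That is a fair limit on size. The all-treated reading is not foreign to the plan, however, because the category rule in Section 12.3.2 points to it.

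Fourth, any single named population would remove the inconsistency, so the all-treated choice is partly a preference. This is also fair. The reason for preferring it is that membership does not depend on what happens after the first dose.

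**Conclusion.** The point holds. One cycle with an early-progression exception and two cycles without one cannot both define the same set, and nothing in the protocol says which sets the ORR denominator. If the two-cycle filter governs and the dropped patients are non-responders, ORR is multiplied by N/(N − k). With the assumed counts that is 12.5% becoming 13.6% (k = 2) or 15.0% (k = 4). N, x and k are all assumptions. Replacement under Section 11.7 could also bring the number dosed above 24. If instead categories 4 to 9 count as failures among all treated patients, there is no inflation.

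A reader might infer that the trial's main conclusion is at risk. It is not. ORR has no hypothesis or threshold, and the example intervals overlap heavily. The Simon decision rests on 2-month PFS, for which Section 11.2 has a separate set (Arm B patients with one dose). Nor do the documents limit ORR to Arm B: neither response definition carries an arm restriction, although pooling or reporting by arm is not stated. The change should be made, but the consequence is confined to a reported secondary rate.

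**What to change.** Put one definition in Sections 11.2 and 12.3.2.

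- **Denominator:** all patients with measurable disease who received at least one dose, reported by arm. Measurable disease is already inclusion criterion 2, so this condition should remove no eligible patient. Dosed patients later replaced for 2-month PFS stay in.
- **Response:** CR and PR only. Categories 3 to 9, including stable disease, progression, early death and not assessed, count as non-response.
- **Supportive rate:** a response-evaluable rate may be shown alongside, with one stated cycle requirement and the early-progression exception.

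The cost is wording in two sections and one tabulation. No new data are needed. The reported ORR may be slightly lower than under the two-cycle filter.
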